4.5.1.7 Colonoscopy by Gastroenterologist

For select patients with known personal history of adenomatous colorectal polyps or colorectal cancer, family history of colon cancer in which a first- and/or second-degree relative has been diagnosed with colorectal cancer at or after the age of 60 years, or

signs or symptoms that could be related to colon cancer as determined by the site investigator or designee, a screening colonoscopy will be conducted. Patients with family history of inherited colon cancer syndromes and/or history of colon cancer in which a first- and/or second-degree relative has been diagnosed with colorectal cancer before the age of 60 years will be excluded from this study.

Colonoscopy must be complete to the cecum, with adequate bowel preparation, and must be performed within the 90-day screening period by a gastroenterologist or his or her designee who is experienced in the colonoscopic diagnosis of colorectal polyps and colorectal cancer. All visualized polyps found at the screening or subsequent colonoscopies will need to be adequately resected.

For select patients (described above), the screening colonoscopy is not required if colonoscopy to the cecum with adequate bowel preparation and adequate resection of all visualized polyps was performed within 1 year of the start of the 90-day screening period, unless the site investigator deems it necessary. Please note that patients with a known personal history of more than three (>3) adenomatous colorectal polyps or a personal history of adenomatous colorectal polyp(s) >2 cm in size will be excluded from this study. This also applies to the polyps visualized during the screening colonoscopy for select patients described above (see also Section 4.1.2).

All patients will be required to undergo a post-treatment colonoscopy within 3 months of discontinuation of study drug. Patients who have polyp(s) found at the post-treatment colonoscopy will need a follow-up colonoscopy performed after an additional 3 years \pm 3 months.

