Protocol GO27826 has been amended as a result of the primary analysis of efficacy and safety (data cutoff 17 April 2017) and an analysis of secondary malignancies (data cutoff 3 July 2017; approximately 94 weeks after the last patient started study treatment). The study did not meet its primary endpoint. A statistically meaningful disease-free survival benefit for vemurafenib treatment was not demonstrated in Cohort 2, as required by hierarchical testing defined in the Statistical Analysis Plan. Safety analysis showed that patients treated in this study had a safety profile consistent with that of patients treated with vemurafenib for unresectable or metastatic melanoma with *BRAF*^{V600} mutation, an approved indication. The analysis of secondary malignancies demonstrated that overall incidences of cutaneous squamous cell carcinoma (including keratoacanthoma) among the vemurafenib-treated patients in this study was similar to the incidence reported in vemurafenib-treated patients with unresectable or metastatic melanoma with *BRAF*^{V600} mutation across studies: approximately 20%.

Changes to the protocol are summarized below:

- The end of study definition has been refined (see Sections 3.2, 6.4, 6.9, and Appendix 1), the length of patient follow-up has been reduced (see Sections 3.1, 3.2, 4.4.2, 4.5, 4.6, 5.1, 5.3, 5.4, 5.5, and Appendix 1), and in patients who had polyp(s) found at the 3-month post-treatment colonoscopy, a further colonoscopy after an additional 3 years is not required (see Sections 4.5, 5.1, and Appendix 1). The last patient in the treatment phase took their last dose of study medication on 14 September 2016. The reduction in the length of follow-up and earlier closure of the study is based on the following considerations:

The primary endpoint was not met; therefore, long-term overall survival data are no longer required, as registration plans are no longer being pursued.

No new safety signals were identified in the primary analysis; therefore, there is no need for additional safety monitoring.

An extensive safety database exists for vemurafenib, with more than 6,200 patients having been treated in company-sponsored clinical trials and a cumulative market exposure to vemurafenib of more than 45,016 patients.

- The reporting of the term “sudden death” has been updated to also require the presumed cause of death (Section 5.3.5.7).
- Event reporting for hospitalization has been clarified (Section 5.3.5.9).

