3.2 END OF STUDY

All patients will be followed for melanoma recurrence or occurrence of new primary melanoma *and overall survival for at least 2 years after Cycle 1, Day 1 of study treatment. Patients may be followed for melanoma recurrence or occurrence of new primary melanoma* for up to 5 years and OS for up to 6 years after Cycle 1, Day 1 of study treatment. Patients who exhibit recurrence of melanoma or a new primary melanoma *during* the study will be followed for OS.

The end of the study is defined as the date of the last patient, last visit, which is expected to occur approximately 6 months after the last patient enrolled has been followed for 2 years after Cycle 1, Day 1 of the study.

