4.5.2.2 Assessments during Study

All assessments must be performed on the day of the specified visit, unless a time window is specified in the Schedule of Assessments (see [Appendix 1](#)). Assessments scheduled on the day of study drug administration should be performed prior to administration of study drug, unless otherwise noted in the Schedule of Assessments. The PRO assessment (EORTC QLQ-C30) should be performed prior to the completion of other study assessments. The timing of interval assessments (such as the head and neck examination and imaging studies) should be calculated from the Cycle 1, Day 1 visit. The frequency of the dermatological examination should be calculated from the date of the first dermatological examination, which should occur after 4 weeks of study drug administration.

For a complete description of study assessments, refer to Section [4.5.1](#) and [Appendix 1](#).

The following assessments will be done during the study:

- Interval medical history, including documentation of new or worsening adverse events: Cycle 1 (Days 8, 15, and 22, each ± 3 days), Cycle 2 (Days 1 and 15, each ± 3 days), Day 1 (± 3 days) of every subsequent 4-week cycle, and at the end-of-treatment visit
- Vital signs: Cycle 1 (Day 15 ± 3 days), Cycle 2 (Days 1 and 15, each ± 3 days), Day 1 (± 3 days) of every subsequent 4-week cycle, and at the end-of-treatment visit
- Physical examinations: Cycle 1 (Day 15 ± 3 days), Cycle 2 (Days 1 and 15, each ± 3 days), Day 1 (± 3 days) of every subsequent 4-week cycle, and at the end-of-treatment visit. Thereafter, physical examinations done by the investigator will be obtained every 13 ± 2 weeks from the last dose of study drug until recurrence of melanoma, occurrence of a new primary melanoma, or *until end* of study (see [Section 3.2](#)), whichever occurs earlier. Height will be obtained at screening only.

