Note: For all patients, as part of the physical examination, a thorough head and neck evaluation to monitor for non-cuSCC, consisting of at least a visual inspection of the oral mucosa and lymph node palpation, must be performed by the site investigator every 13 ± 2 weeks during the study drug treatment period. Once a patient completes the treatment period or discontinues study drug early, a thorough evaluation of the head and neck by the study investigator will be performed at the end-of-treatment visit as part of the physical examination. Once a patient completes the treatment period or discontinues study drug early, a thorough head and neck evaluation to monitor for non-cuSCC will occur (as part of the physical examination for patients who continue to have physical examinations) at 13 ± 2 weeks and 26 ± 2 weeks from the last dose of study drug. For patients who no longer require physical examinations, the head and neck examination will occur independently at 13 ± 2 weeks and 26 ± 2 weeks from the last dose of study drug (except in the case of withdrawal of consent or loss to follow-up).

Patients with signs or symptoms consistent with head and neck cancer as determined by the site investigator will have a complete evaluation of the head and neck by a head and neck surgeon/otorhinolaryngologist or his or her designee who is experienced in the diagnosis and management of SCC of the head and neck: every 26 ± 2 weeks during the study drug administration period. Once a patient completes the treatment period or discontinues study drug early, a complete evaluation of the head and neck by a head and neck surgeon/otorhinolaryngologist will be performed at 26 ± 2 weeks after the last dose of study drug (except in the case of withdrawal of consent or loss to follow-up).

- All patients will have a colonoscopy to the cecum, with adequate bowel preparation, by a gastroenterologist or his or her designee who is experienced in the colonoscopic diagnosis of colorectal polyps and colorectal cancer within 3 months of discontinuation of study drug. All polyps found at any of the colonoscopies will need to be adequately resected.
- Hematology: Day 1 (± 3 days) of each cycle and the end-of-treatment visit
- Serum chemistry and liver function tests: Cycle 1 (Days 8, 15, and 22, each ± 3 days), Cycle 2 (Days 1 and 15, each ± 3 days), Day 1 (± 3 days) of every subsequent 4-week cycle and at the end-of-treatment visit

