5.1.2.3.4 Colorectal Polyps

For select patients with known personal history of adenomatous colorectal polyps or colorectal cancer, family history of colon cancer in which a first- and/or second-degree relative has been diagnosed with colorectal cancer at or after the age of 60 years, or signs or symptoms that could be related to colon cancer as determined by the site investigator or designee, a screening colonoscopy will be conducted. Patients with family history of inherited colon cancer syndromes and/or history of colon cancer in which a first- and/or second-degree relative has been diagnosed with colorectal cancer before the age of 60 years will be excluded from this study.

Colonoscopy must be complete to the cecum, with adequate bowel preparation, and must be performed within the 90-day screening period by a gastroenterologist or his or her designee who is experienced in the colonoscopic diagnosis of colorectal polyps and colorectal cancer. All visualized polyps found at the screening or subsequent colonoscopies will need to be adequately resected. For select patients (described above), the screening colonoscopy is not required if colonoscopy to the cecum with adequate bowel preparation and adequate resection of all visualized polyps was performed within 1 year of the start of the 90-day screening period, unless the site investigator deems it necessary. Please note that patients with a personal history of more than three (>3) adenomatous colorectal polyps or a personal history of adenomatous colorectal polyp(s) >2 cm in size will be excluded from this study; this also applies to the screening colonoscopy for the select patients described above (see also Section 4.1.2).

All patients will be required to undergo a post-treatment colonoscopy within 3 months of discontinuation of study drug.

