Appendix 1 Schedule of Assessments (cont.)

prior to the start of the 90-day screening period and found to be normal, need not be repeated at screening.

- ^p For patients with personal history of adenomatous colon polyps or colorectal cancer, family history of colon cancer in which a first- and/or second-degree relative has been diagnosed with colorectal cancer at or after the age of 60 years, or signs or symptoms that could be related to colon cancer as determined by the site investigator or designee, colonoscopy to the cecum, with adequate bowel preparation, will be performed by a gastroenterologist or his or her designee who is experienced in the colonoscopic diagnosis of colorectal polyps and colorectal cancer (within the 90-day screening period). For select patients (described above), the screening colonoscopy is not required if colonoscopy to the cecum with adequate bowel preparation and adequate resection of all visualized polyps was performed within 1 year of the start of the 90-day screening period, unless the site investigator deems it necessary. All patients must have colonoscopy within 3 months of discontinuation of study drug. All polyps found at the screening or subsequent colonoscopies will need to be adequately resected. Please note that a patient with a personal history of more than three (> 3) adenomatous colorectal polyps or a personal history of adenomatous colorectal polyp(s) > 2 cm in size will be excluded from this study; this also applies to the screening colonoscopy for the select patients described above (see Section 4.1.2).
- ^q Stool sample will be collected at screening, Cycle 6, Day 1 (± 2 weeks), and at the end-of-treatment visit (± 2 weeks). If the stool occult sample is positive at screening, the patient must be cleared for study inclusion by a gastroenterologist or appropriately trained designee.
- ^r Includes hemoglobin, hematocrit, platelet count, WBC count, WBC differential (ANC), lymphocyte, monocyte, eosinophil, and basophil counts, and other cell counts.
- ^s Includes sodium, potassium, chloride, bicarbonate, glucose, BUN or urea, creatinine, calcium, total bilirubin, albumin, ALT, AST, alkaline phosphatase, phosphorus, magnesium, LDH, and uric acid.
- ^t If a patient discontinues study drug early, a serum pregnancy test will be performed at 12 ± 2 weeks and 26 ± 2 weeks after the last dose of study drug (except in the case of withdrawal of consent or loss to follow-up).

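### Protocol Section 4.5.1.7 still mandates a 3-year repeat colonoscopy that Version 10 dropped and that Sections 4.5.2.2, 5.1.2.3.4 and Appendix 1 do not contain

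*Protocol*

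**What the plan says.** Four current places in the protocol deal with colonoscopy after treatment.

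- **Section 4.5.1.7** requires a colonoscopy within 3 months of stopping study drug and then adds: "Patients who have polyp(s) found at the post-treatment colonoscopy will need a follow-up colonoscopy performed after an additional 3 years", ± 3 months.
- **Section 4.5.2.2** lists the colonoscopy within 3 months of stopping and closes the item with "All polyps found at any of the colonoscopies will need to be adequately resected". It sets no repeat.
- **Section 5.1.2.3.4**, the section on colorectal polyps, ends at "All patients will be required to undergo a post-treatment colonoscopy within 3 months of discontinuation of study drug". It sets no repeat.
- **Appendix 1, footnote p** says "All patients must have colonoscopy within 3 months of discontinuation of study drug" and covers resection of polyps. It sets no repeat.

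The rationale at the front of Version 10 states the intention for patients found to have polyps: "a further colonoscopy after an additional 3 years is not required". It points to Sections 4.5, 5.1 and Appendix 1 as the places where this is carried out, and Section 4.5 includes 4.5.1.7.

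Section 4.5.2.2 also says "For a complete description of study assessments, refer to Section" 4.5.1 and Appendix 1, so sites are sent to both.

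**The concern.** The two places that sites are told to read together for the full list of assessments give different instructions on a safety procedure. Section 4.5.1.7 makes the 3-year repeat mandatory for a defined group, and Appendix 1 does not schedule it.

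A site working from 4.5.1.7 could send a patient for bowel preparation and an invasive examination that the sponsor has decided is not needed. A site working from Appendix 1 would skip a procedure that 4.5.1.7 still requires, and could be recorded as deviating. Patients in the same situation could be handled differently by site, on a matter tied to a listed adverse event of special interest (gastrointestinal polyps, Section 5.2.3). For later-enrolled patients the repeat would also fall after the study has closed.

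Nothing here bears on the efficacy analyses, power or Type I error.

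**Working it through.** **Text comparison**

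| Place in current protocol | Colonoscopy within 3 months of stopping | Repeat at 3 years if polyps found |
|---|---|---|
| 4.5.1.7 | Required | Required, ± 3 months |
| 4.5.2.2 | Required | Absent |
| 5.1.2.3.4 | Required | Absent |
| Appendix 1, footnote p | Required | Absent |
| Version 10 rationale | – | Stated as not required |

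The first four rows are all current text, so the disagreement does not depend on the summary of changes. That summary suggests how it arose: it shows the repeat sentence struck from 4.5.2.2 and 5.1.2.3.4 and lists no change to 4.5.1.7. Footnote p mentions later colonoscopies only in connection with resecting polyps, which does not create a 3-year visit.

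**When the repeat would fall**

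Inputs:

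- Secondary-malignancy data cutoff 3 July 2017, about 94 weeks after the last patient started treatment (Version 10 rationale).
- "The last patient in the treatment phase took their last dose of study medication on 14 September 2016" (Version 10 rationale).
- End of study is "expected to occur approximately 6 months after the last patient enrolled has been followed for 2 years" after Cycle 1, Day 1 (Section 3.2), i.e. 24 + 6 = 30 months after the last patient's start.
- Post-treatment colonoscopy 0 to 3 months after last dose; repeat 36 ± 3 = 33 to 39 months after that (Section 4.5.1.7).
- Assumption: 52 weeks is taken as 12 months.

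Steps:

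1. Last patient's start: 3 July 2017 − 94 × 7 = 658 days gives about 14 September 2015.
2. Expected end of study: 14 September 2015 + 30 months gives about 14 March 2018.
3. Repeat window measured from last dose: (0 to 3) + (33 to 39) = 33 to 42 months.
4. Repeat window for a 52-week completer, from Cycle 1, Day 1: 12 + (33 to 42) = 45 to 54 months.
5. Last-enrolled patient, last dose 14 September 2016: + 33 months = 14 June 2019; + 42 months = 14 March 2020. Against 14 March 2018 that is 15 to 24 months late.
6. Earliest possible repeat for any patient (drug stopped at once, colonoscopy at once): 0 + 0 + 33 = month 33. For the last-enrolled patient the study ends at month 30, so even then the repeat is outside it.

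For completers generally, working back from the end of study:

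| Start of treatment | Position of the 45–54 month window |
|---|---|
| After about 14 June 2014 (14 March 2018 − 45 months) | Wholly after end of study |
| About 14 September 2013 to 14 June 2014 | Straddles end of study |
| Before about 14 September 2013 (14 March 2018 − 54 months) | Wholly before end of study |

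Version 10 cites a 3 July 2017 cutoff, so it cannot be earlier than that date. For completers who started before about January 2013 (3 July 2017 − 54 months = 3 January 2013), the window had closed before Version 10 existed. For patients who stopped early, all of these start dates move later by up to 12 months.

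**The case against.** The strongest reply is that this is an editing slip which the document already resolves. The rationale at the front of Version 10 says the repeat is not required and names Section 4.5, so a site holding the protocol has the answer. The other sections are silent on a repeat and do not forbid it, so a conditional step in 4.5.1.7 and silence elsewhere could be read together. In practice, the sentence could mislead in-study scheduling only between Version 10 (July 2017 at the earliest) and about March 2018, roughly 8 months. The correction also may not be free: Section 9.5 requires ethics approval for protocol changes unless they address an immediate hazard or are purely logistical or administrative, and Section 9.3 allows for about 200 centers.

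Much of this is right as description. The rationale does settle the intent. The explicit contradiction is between the rationale and 4.5.1.7, while the other three sections simply omit the repeat. The Version 10 date does remove the earliest completers.

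It does not remove the problem. A schedule of assessments is meant to be complete, so leaving out a mandatory invasive procedure is a real disagreement with the section that mandates it. Sites work from the operative sections, and the one that describes colonoscopy still carries the instruction. That the intent is clear is a reason to make the text follow it.

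**Conclusion.** The concern holds. Section 4.5.1.7 keeps a mandatory 3-year repeat colonoscopy that the sponsor has dropped and that the other current sections do not contain.

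Its reach is limited to patients with polyps at the post-treatment colonoscopy. The documents give no count, so the number affected is unknown. The 15 to 24 months for the last-enrolled patient is the extreme case; some earlier completers had a window that fell inside the study, where the sentence could prompt a procedure while the study was open. The dates rest on the approximate 94-week interval, the expected 30-month end of study and 52 weeks taken as 12 months.

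This should be corrected because it concerns an invasive safety procedure. It does not threaten the trial's conclusions.

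**What to change.** Delete the last sentence of Section 4.5.1.7, so that the section ends at the colonoscopy within 3 months of stopping study drug and agrees with 4.5.2.2, 5.1.2.3.4, Appendix 1 footnote p and the Version 10 rationale. Notify sites that no 3-year repeat is required by the protocol. With the repeat gone, no rule for collecting post-study colonoscopy results is needed.

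The cost is one sentence and a site notice. Whether the deletion counts as administrative under Section 9.5 is for the sponsor to determine; a clarification letter citing the Version 10 rationale can go out in the meantime. Data already collected and the planned analyses are unchanged.

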4.5.1.8 Laboratory Assessments

Blood samples for hematology, coagulation screening studies, liver function tests, serum chemistry, pregnancy test, and hepatitis B and C serology will be analyzed at the study site's local laboratory. Stool for occult blood will be analyzed at the local site. Blood and tumor tissue samples for biomarker and PK studies will be sent to one or several Roche-designated central laboratories or to the Sponsor for analysis. Instruction manuals and supply kits will be provided for all central laboratory assessments. All screening laboratory assessments should be obtained prior to initiation of study drug at Cycle 1, Day 1.

Laboratory assessments will include the following:

- Hematology: Hemoglobin, hematocrit, platelet count, WBC, WBC differential (absolute neutrophil count, lymphocyte, monocyte, eosinophil, and basophil counts and other cells)
- Coagulation: PT, INR, and aPTT
- Serum chemistry: urea (BUN), creatinine, sodium, potassium, chloride, bicarbonate, glucose, phosphorus, magnesium, total calcium, serum albumin, LDH, and uric acid

- Liver function tests: ALT, AST, total bilirubin, and alkaline phosphatase
- Pregnancy test: All women of childbearing potential (including those who have had a tubal ligation) will have a serum pregnancy test at screening and every 3 cycles (i.e., Cycles 3, 6, 9, and 12 or every 12 ± 2 weeks), starting from Cycle 1, Day 1, and at 12 ± 2 weeks and 26 ± 2 weeks after the last dose of study drug. Urine pregnancy tests will be performed as needed. If a urine pregnancy test is positive, it must be confirmed by a serum pregnancy test.
- Viral serology/detection: Hepatitis B (hepatitis B surface antigen [HBsAg] and total hepatitis B core antibody [anti-HBc]) and HCV antibody
- Stool for occult blood

4.5.1.9 ***BRAF*^{V600} Mutation Testing**

Assessment of *BRAF*^{V600} mutation status of primary tumor tissue will be investigated using the **cobas**[®] BRAF V600 Mutation Test. A formalin-fixed paraffin-embedded (FFPE) tumor block or at least five serially cut, unstained tumor tissue slides (5 μm -thick sections) from one block will be collected at screening from consented patients. Patients whose tumors test positively for the *BRAF*^{V600} mutation will be eligible for enrollment in the clinical study if they meet other eligibility criteria.

For patients whose tumors undergo **cobas**[®] testing at a Roche-designated central testing facility, tumor blocks from the patients who are not eligible for the study will be returned after screening has been completed. For patients eligible for the study, additional testing will be performed at Roche or a centralized specialty laboratory (see Section 4.5.1.12, Exploratory Biomarker Assessments). These additional investigations will be performed retrospectively and will not influence patient's eligibility for this study.

4.5.1.10 **Pharmacokinetic Assessments**

Plasma concentrations of vemurafenib will be measured in a central laboratory using a validated assay. Venous blood samples (2 mL) will be collected in sodium heparin according to the Schedule of Pharmacokinetic Assessments (Section 4.5.2.2 and Appendix 2).

For all scheduled and unscheduled PK samples, the date and time of the last dose of study drug should be specified on the eCRF along with the actual time of the PK blood draw. The procedures for the collection, handling, and shipping of PK samples can be found in the laboratory manual.

The total volume of blood collected for PK assessments will be approximately 16 mL for Cycle 1 and an additional approximately 26 mL for patients who complete the full 52-week treatment regimen. Unscheduled PK samples are not considered in this calculation (see Section 4.5.2.2).

